3.2.1. Co-Primary Efficacy Endpoint

In the 3rd line+ population intended for regulatory submissions in the US and jurisdictions on which the 3rd line+ eribulin label applies, the co-primary endpoints are:

- ORR (confirmed CR + confirmed PR) according to RECIST v1.1 guidelines, as assessed by the IRC.
- PFS according to RECIST v1.1 guidelines, as assessed by the IRC.

3.2.2. Key Secondary Efficacy Endpoint

The key secondary efficacy endpoint subject to Type I error control is OS.

3.2.3. Other Secondary Efficacy Endpoints

Other secondary efficacy endpoints are considered supportive and will not be subject to overall Type I Error control. These endpoints are:

- PFS according to RECIST v1.1 guidelines, as assessed by the local Investigator's review.
- ORR (confirmed CR + confirmed PR) according to RECIST v1.1 guidelines, as assessed by the local Investigator's review.
- Clinical Benefit Rate (CBR) [proportion of patients with confirmed CR, confirmed PR, or stable disease (SD) ≥6 months] according to RECIST v1.1 guidelines, as assessed by (i) the IRC and (ii) the local Investigator's review.
- Disease control rate (DCR; number of patients with confirmed CR, confirmed PR, or SD) according to RECIST v1.1 guidelines, as assessed by (i) the IRC and (ii) the local Investigator's review.
- Time to response, as assessed by (i) the IRC and (ii) the local Investigator's review.
- Duration of response, as assessed by (i) the IRC and (ii) the local Investigator's review.

3.2.4. Secondary Safety Endpoints

These will include:

- Type, frequency and severity of AEs (including serious adverse events [SAEs], adverse events of Special Interest [AESIs]).
- Laboratory abnormalities.
- Vital signs.

Additionally, signs and symptoms of anaphylaxis will be captured and summarized in accordance with guidance provided by the Second Symposium on the Definition of Anaphylaxis. Evaluation of liver parameters will be made according to the evaluation of Drug-induced Serious Hepatotoxicity (eDISH) criteria; this requires a log-log plots of alanine aminotransferase (ALT)/aspartate aminotransferase (AST) vs total bilirubin to identify potential cases of concern, followed by time course plots of all the identified potential cases.

3.2.5. Exploratory Efficacy Endpoints

- Efficacy as measured by PFS, ORR and OS in each exploratory subgroup (Demographic and Baseline Characteristics, Disease History and Progression Status).
- Response, as assessed by iRECIST (2017) in those patients who continue treatment despite progression.
- EORTC-QLQ-C30 QoL change from baseline to the end of each treatment cycle.
- The FACT-B and EQ-5D change from baseline to the end of each treatment cycle.

The following endpoints will be analyzed in a separate plan:

- Relationship between ORR, PFS, or OS and baseline biomarkers including ER status, PgR status or CXCR4 expression levels.
- Relationship between ORR, PFS, or OS and exploratory biomarkers (from tumor tissue or blood) including cytokines (e.g. IFN-gamma), immune cells profile, and ribonucleic acid (RNA) expression.
- Plasma concentration of balixafortide and potential metabolites (PK analysis set).

3.3. Treatments

Patients will be randomized as follows:

3.3.1. Balixafortide + eribulin

Patients will receive balixafortide + eribulin treatment. Balixafortide will be administered on Days 1–3 and Days 8–10 and eribulin will be administered on Days 2 and 9 of each 21-day cycle.

Day	1	2	3	4	5	6	7	8	9	10	11	12	13	14	15	16	17	18	19	20	21
POL6326	1	2	3	trea	tmen	t bre	ak	8	9	10	treatment break										
Eribulin		2		trea	tmen	t bre	ak		9	treatment break											

3.3.2. Eribulin monotherapy

Patients will receive eribulin monotherapy; Eribulin will be administered on Days 2 and 9 of each 21-day cycle.

Day	1	2	3	4	5	6	7	8	9	10	11	12	13	14	15	16	17	18	19	20	21
Eribulin		2		trea	atme	nt bre	eak		9					tre	atme	nt br	eak				

Balixafortide will be administered, at a dose of 5.5 mg/kg, intravenously over 2 hours ± 10 min; however, the infusion time of balixafortide can be increased to a maximum of 3 hours at the discretion of the treating physician, for reasons of patient tolerability (i.e. to manage infusion related reactions). Eribulin should be administered intravenously as the ready to use solution at a dose of 1.4 mg/m² over 2 to 5 minutes on Days 2 and 9 of each 21-day cycle. **note:** this dose is expressed as the salt, eribulin mesylate; however, in some countries this dose is expressed as the

3.4. Dose Adjustment/Modifications

3.4.1. Dose Modification Balixafortide

In the event of significant treatment-related toxicity, balixafortide + eribulin dosing may be modified in two ways:

- Within a cycle: dosing interruption during a given treatment cycle until there is adequate recovery;
- Between cycles: administration of the next cycle may be delayed due to persistent toxicity.

Patients that discontinue from balixafortide treatment due to treatment-related toxicity are to attend an EoT Visit within 7 days after discontinuation, the 30-day safety follow-up visit for assessments and recording of AEs and concomitant medications, and the Long-term Follow-up visits.

3.4.2. Dose Modification Eribulin

The dose of eribulin can be decreased or modified according to the US regulatory label for eribulin as detailed in the protocol.

Categorical variables will be presented as frequency counts and percentages. A row or column denoted 'missing' will be included in count tabulations where necessary to account for dropouts and missing values. Percentages will be rounded to 1 decimal place and the percent will be suppressed when the count is zero. The denominator will be the number of patients in that dose schedule within the analysis set of interest unless otherwise noted.

Time-to-event variables will be analyzed using the Kaplan-Meier (KM) method. The KM estimates for quartiles and the confidence interval (CI) for the median will be presented as described below. Kaplan-Meier curves will also be plotted.

Time-to-event variables will be also analyzed by a Cox proportional hazards model.

Data listings will be created to support each table and to present all data. Data listings will be presented by treatment arm and patient number.

Although this is an open label trial, grouped evaluation of randomized treatment arms will be performed only for the pre-planned interim efficacy analyses and DSMB safety reviews as described in Section 8.0 of this document and in the DSMB charter. In order to protect the integrity of the trial and the robustness of the results, project team members, both Polyphor Ltd. and CRO personnel, will not evaluate, formally or informally, data grouped by randomized treatment arm as data are accruing over time. Procedures relating to the execution of pre-planned interim efficacy analyses and DSMB safety reviews are described in the DSMB Charter.

Important study variables to be used in the analysis, defined as follows:

- Age: Recorded as "Age" in the eCRF instead of the Date of Birth.
- Baseline:
 - For *efficacy evaluations*, the last available assessment before or at date of randomization is taken as "baseline" value or "baseline" assessment. For PRO endpoints, baseline is the mean of the PROs taken at screening and at last visit before first treatment administration with no imputation done if any of them is missing.
 - For *safety evaluations* (such as laboratory and vital signs), the last available assessment before first study treatment administration is taken as "baseline" value or "baseline" assessment. For patients who have not received any study treatment, the baseline will be the last assessment performed before randomization.
 - If patients have no value as defined above, the baseline result will be missing.

- Study day: For post-treatment events, study day is calculated as (event/assessment date date of Day 1) + 1. For pre-treatment events, study day is calculated as event/assessment date date of Day 1. There is no study day zero. Day 1 is the date of Cycle 1 Day 1 for balixafortide + eribulin arm, while it is the date of Cycle 1 Day 2 1 for eribulin arm:
 - Balixafortide + eribulin arm: Cycle 1 Day 1.
 - Eribulin arm: (Cycle 1 Day 2) 1.
- Body Mass Index (BMI) (kg/m²) is defined as [Weight(kg)] / [Height(m)]².
- Body Surface Area (BSA) (m²) is defined as $\sqrt{\text{Height}(\text{cm}) * \text{Weight}(\text{kg})/3600}$.

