7.3 Treatment Period—Balixafortide + Eribulin Treatment Arm Only

7.3.1 Cycle 1

7.3.1.1 Cycle 1 Day 1

Patients will start study medication within 3 days from randomization as outlined in the Study Schedule (Section 1.1).

The following procedures and assessments will be performed following randomization:

Before Balixafortide Administration:

- Patient reported health outcome QoL questionnaires (see Section 11.3).
- Targeted physical examination (see Section 9.6).

Protocol No.: POL6326-009

Version 3.0

 Vital signs (resting BP, respiratory rate, pulse rate, and body temperature; see Section 9.7).

- Weight
- ECOG performance status (see Section 9.6).
- AE reporting (see Section 9.2).
- Concomitant therapy/medications taken since the Screening Visit (see Section 5.4.1).
- Clinical laboratory tests (hematology, chemistry, and urinalysis; see Section 9.9); blood test results must be available within 24 hours prior to study drug administration.
- Urine pregnancy test for women of child bearing potential (see Section 5.4.5.1).
- 12-lead ECGs, 2 baseline ECG recordings taken within 1 hour prior to administration of balixafortide (see Section 9.8).
- Blood samples for immunogenicity taken immediately before starting balixafortide infusion (see Section 11.1).
- Blood samples for exploratory biomarkers in all patients taken immediately before starting balixafortide infusion (see Section 11.2.2).
- IWRS/IRT registration.

Balixafortide Administration (see Section 6.1).

Immediately After Completing Balixafortide Infusion:

• Blood samples for exploratory biomarkers in all patients (see Section 11.2.2).

Patients at Selected Sites Only:

For patients at selected sites, the following additional assessments will be performed:

• Blood samples for other exploratory biomarkers in patients at selected sites (see Section 11.2.2).

7.3.1.2 Cycle 1 Day 2

Before Balixafortide Administration:

- AE reporting (see Section 9.2).
- Concomitant therapy/medications taken since the previous visit (see Section 5.4.1).
- IWRS/IRT registration.
- 12-lead ECG before starting balixafortide infusion (see Section 9.8).
- Blood sample for PK taken immediately before starting balixafortide infusion, see Section 10.1.

Balixafortide Administration (see Section 6.1).

After Balixafortide Administration, but Before Administration of Eribulin:

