11.3 Patient Reported Outcomes

Patient reported outcomes (PROs) of health-related QoL and health status will be assessed using the EORTC-QLQ-C30, FACT-B and EQ-5D instruments. Patients will complete each instrument at the Screening Visit and at the EoT visit. Patients on the balixafortide + eribulin treatment arm will also complete each instrument pre-dose on Day 1 of each cycle. Patients on the eribulin monotherapy treatment arm will also complete each instrument pre-dose on Day 2 of each cycle. These instruments should be completed in the same sequence at each scheduled assessment.

During the study treatment phase, patients must complete these instruments in clinic (cannot be taken home) and prior to having any clinical assessments, drug dosing, diagnostic testing, and to any discussion of their progress with healthcare personnel at the site. Interviewer administration in clinic may be used under special circumstances (e.g. patient forgot their glasses or feels too ill).

The EORTC-QLQ-C30 is a validated instrument to measure QoL and assess symptoms and side effects of treatment and their impact on everyday life. The instrument is composed of 5 multi-item functional scales (physical, role, social, emotional and cognitive functioning), a global health status/QoL scale, 3 symptom scales (fatigue, nausea/vomiting and pain), and 6 single items (financial difficulties, appetite loss, diarrhea, constipation, insomnia and dyspnea).

PROs of health-related QoL and health status will be assessed using the FACT-B and EQ-5D instruments. The FACT-B and EQ-5D will be given to the patient in the appropriate language.

The EQ-5D consists of two parts, the EQ-5D descriptive system and the EQ Visual Analogue scale (EQ VAS). The descriptive system comprises 5 dimensions: mobility, self-care, usual activities, pain/discomfort, anxiety/depression. Each dimension has 5 levels: no problems, slight problems, moderate problems, severe problems, and extreme problems. The EQ VAS records the patient's self-rated health visual analogue scale with endpoints labelled 'the best health you can imagine' and 'the worst health you can imagine'.

FACT-B is a self-administered questionnaire designed for patient suffering from BC. It consists of 5 subscales (physical wellbeing, social/family wellbeing, emotional wellbeing, functional wellbeing, breast subscale)

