12.2.2 Analysis Sets

The following analysis sets are defined for the Overall Population:

- Intention-to-treat (ITT) Population is defined as all randomized patients. Efficacy data in this population will be summarized by randomized treatment. The co-primary endpoint PFS and key secondary efficacy endpoint OS will use the ITT population. Patients will be analyzed by the treatment arm to which they are randomized.
- **Safety Population** is defined as all randomized patients who receive at least one dose (or partial dose) of study medication. Patients will be analyzed by the treatment arm received, based on the first dose of study drug.
- Response Evaluable Population will be used to evaluate disease response. The Response Evaluable Population includes all patients who are randomized in the study with measurable disease by RECIST v1.1 (as determined by the Investigator). The coprimary endpoint analysis of ORR and other secondary endpoint analyses of CBR and duration of response will be conducted using the Response Evaluable Population. Patients will be analyzed by the treatment arm to which they are randomized.
- Patient Reported Outcome (PRO) Population is defined as all patients in the ITT Population where the patient has at least one post randomization PRO value. Patients will be analyzed by the treatment arm to which they are randomized.

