4.3.8. Patient Reported Outcome Set (3rd Line+)

The Patient Reported Outcome (PRO) set $(3^{rd} line+)$ is defined as all randomized patients in the $3^{rd} line+$ population where the patient has at least one post-baseline PRO value (e.g. EORTC

questionnaire, EQ-5D or FACT-B). Patients will be analyzed by the treatment arm to which they are randomized.

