At each assessment point, summary statistics of absolute scores and changes from baseline will be calculated by treatment arm for each scale for both the raw score and the linear transformed score. The baseline result will be the mean of the screening visit score and the score at last assessment prior to dosing. Summary tables and boxplots of the score by visit and treatment arm will be presented. The best and worst changes from baseline and associated time points will also be summarized using descriptive statistics. For functional scales and global health status, best changes from baseline are positive changes; while for symptom scales/items, best changes are negative changes.

The percentage of patients missing the entire questionnaire will be summarized and reason it is missing will be listed by treatment arm.

If more than 50% of questions are unanswered within a subscale at a particular timepoint, the value for the subscale will be set to missing. If less than 50% of questions are unanswered, the

sum of the scores for the answered questions will be taken and scaled up in relation to the number of questions in the scale answered or not.

The change from baseline for the linear transformed score will be compared between treatment arms for the PRO (3rd line+) set using mixed model repeated measures (MMRM) analysis with fixed effect terms for treatment arm, visit, treatment arm by visit interaction, the randomization stratification factors and also with baseline score as a covariate. Patient will be included as a random effect. The default estimation method of Restricted Maximum Likelihood (REML) and the Kenward-Roger (KR) option for degrees of freedom will be used. An unstructured covariance matrix will be used to model the within-patient error. If the fit of the unstructured covariance structure fails to converge, the following covariance structures will be tried in order until convergence is reached: Toeplitz with heterogeneity, autoregressive with heterogeneity, toeplitz, and autoregressive. A summary table will present number of subjects in each treatment group at each visit, LSMeans by treatment arm by visit, along with the difference in LSMeans, standard error, 95% CI and 2-sided p-value.

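### The PRO baseline requires both the screening and the pre-dose questionnaire, so a patient with one usable score drops out of the baseline-dependent PRO analyses

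*SAP*

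**What the plan says.** The definition of baseline in SAP section 4 treats PRO endpoints separately from other efficacy endpoints. For the others, baseline is the last assessment up to the date of randomization. For PROs it is the mean of two scores, one from screening and one "at last visit before first treatment administration with no imputation done if any of them is missing". The same list closes with a general rule: "If patients have no value as defined above, the baseline result will be missing".

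SAP 8.5.1 restates this for the EORTC-QLQ-C30: "The baseline result will be the mean of the screening visit score and the score at last assessment prior to dosing". It gives no rule for a patient who has only one of the two. Its missing-data rule concerns unanswered items within a subscale.

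The repeated-measures model (MMRM) in 8.5.1 analyses change from baseline, adjusting for "the randomization stratification factors and also with baseline score as a covariate". SAP 8.5.2 and 8.5.3 apply the same approach to the EQ VAS and to the FACT-B scores.

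Entry to the PRO set does not depend on baseline. SAP 4.3.8 takes randomized 3rd line+ patients "where the patient has at least one post-baseline PRO value". Protocol 12.2.2, for the overall population, takes "all patients in the ITT Population where the patient has at least one post randomization PRO value".

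On timing, Protocol 11.3 says that combination-arm patients "will also complete each instrument pre-dose on Day 1 of each cycle"; control patients do so on Day 2. Protocol 7.3.1.1 lists the Cycle 1 Day 1 questionnaire under the line "The following procedures and assessments will be performed following randomization", and 7.4.1 does the same for the control arm.

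**The concern.** Requiring two questionnaires for a baseline discards data already collected. A patient who completed one of them and every later form has an undefined change score and a missing covariate, so the model cannot use any of that patient's visits. The patient is still counted in the PRO set, so the set and the patients behind the main PRO estimates would differ.

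The rule is also stricter than the plan's own practice elsewhere. Within a subscale, SAP 8.5.1 and 8.5.3 scale up the score when fewer than half the items are unanswered, whereas a patient with one complete questionnaire out of two gets no baseline.

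A smaller question is timing. The second score is taken after allocation in an open-label trial, so a reaction to the assigned arm could enter the baseline.

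**Working it through.** **Which analyses lose the patient.** Reading the SAP sections side by side:

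- Need the baseline: change-from-baseline summaries and best/worst change (8.5.1); the improved/stable/worsened classification, which requires at least two change scores (8.5.1); the MMRMs for EORTC-QLQ-C30 (8.5.1), EQ VAS (8.5.2) and FACT-B (8.5.3).
- Do not need it: membership of the PRO set (4.3.8); absolute-score summaries (8.5.1, 8.5.3); the generalized estimating equations for the EQ-5D descriptive system, whose model in 8.5.2 has only treatment, visit and their interaction.

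**Size.** The documents give no expected completion rate and no figure for this loss, so there is nothing to reproduce. As an illustration, let *m* be the share missing each questionnaire (assumed), with the two independent. Use N = 320, the planned 3rd line+ number (Protocol 12.3.1), as a stand-in for the PRO set, whose size is not known.

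- No baseline under the SAP rule: 1 − (1 − m)²
- No baseline if one score is accepted: m²
- Usable score discarded: the difference, 2m(1 − m)

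| m (assumed) | SAP rule | One score accepted | Usable score discarded |
|---|---|---|---|
| 2% | 4.0% (12.7 patients) | 0.04% (0.1) | 3.9% (12.5) |
| 5% | 9.8% (31.2) | 0.25% (0.8) | 9.5% (30.4) |
| 10% | 19.0% (60.8) | 1.0% (3.2) | 18.0% (57.6) |
| 15% | 27.8% (88.8) | 2.3% (7.2) | 25.5% (81.6) |

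**Correlated missingness.** The same patient, site and device produce both forms, so independence is unlikely. With correlation ρ between the two missingness indicators, the probability that both are missing is m² + ρm(1 − m), and that at least one is missing is 2m minus this.

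- m = 10%, ρ = 0.5: both missing 0.01 + 0.5 × 0.09 = 0.055; at least one missing 0.20 − 0.055 = 0.145; recovered by accepting one score 0.145 − 0.055 = 0.09.
- m = 10%, ρ = 1: both missing 0.10; at least one missing 0.10; recovered 0.

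For non-negative correlation, the table values are therefore upper values at each assumed rate.

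**Timing of the second score.** Suppose that knowing the arm shifts the pre-dose score by d points between arms (assumed). The averaged baseline then carries d/2. A raw change score is biased by d/2 in size. In the MMRM, baseline is also a covariate, so the treatment contrast is the same as for the raw post-baseline score and moves by b × d/2, where b is the slope of the post-baseline score on baseline. For an assumed d of 4 points, raw change moves by 4/2 = 2 points and the model estimate by 2b. Against this stands the 5-point threshold in SAP 8.5.1. The documents give neither d nor b.

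**The case against.** The text could be read leniently: declining to impute might mean averaging whichever score exists. The next rule in the list, which makes baseline missing when there is no value as defined, points the other way, and 8.5.1 offers no single-score option. If the lenient rule was intended, the wording still needs to say so, because two programmers could code it differently.

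A reader might infer that patients are lost for no reason. That goes too far. Averaging two pre-treatment scores reduces measurement error, and requiring both keeps one definition for everyone. This benefit is real, though small beside discarding a patient's whole follow-up.

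A reader might also take 19% as the expected loss. It rests on an assumed 10% rate and on independence. Protocol 11.3 requires treatment-phase forms to be completed in clinic and allows interviewer help, so a low pre-dose rate is plausible. SAP 8.5.1 also summarizes wholly missing questionnaires, with reasons listed by arm, so the loss would be partly visible. That those who miss a form are sicker is plausible but not shown in the documents.

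The strongest tempting reading is that the reaction to allocation is subtracted from the treatment effect. The documents do not support that at full size: the post-randomization score has half weight and acts in the model only through the baseline slope. That patients know their arm when they complete the form is a fair inference from the open-label design, but it is not stated. Completing the form before clinical assessments and discussion of progress limits staff influence without concealing the arm.

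**Conclusion.** The concern holds as a minor point about exploratory analyses. As written, the SAP sets the PRO baseline to missing unless both questionnaires exist, and so removes patients with one usable score from the baseline-dependent analyses listed above. Up to about 4% to 28% would have no baseline at an assumed 2% to 15% missing per questionnaire under independence, and fewer with positive correlation. Neither the rates nor the independence comes from the documents.

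SAP 8.5 places PROs outside Type I error control, and no co-primary or key secondary test uses this baseline. The post-randomization timing of the second score is a secondary note of unknown size. It does not justify replacing the two-score baseline with screening alone as the main definition: screening may be up to 21 days before randomization, with up to 3 more days to first dose, so that score could be 21 + 3 = 24 days old at treatment start.

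**What to change.** In SAP section 4, and in the matching sentence of 8.5.1, define the PRO baseline as the mean of the available pre-treatment scores, using the single score when only one exists and leaving baseline missing only when neither does. Report by arm how many patients have two, one or no baseline scores.

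Add a sensitivity analysis of the MMRMs using the screening score alone as baseline, to show whether the timing of the second score matters.

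The cost is SAP wording and one extra set of model runs; no new data are needed. Baseline precision becomes slightly uneven, since a single score is noisier than a mean of two. The main change also leaves the timing question open: a patient with only the pre-dose score would have a baseline taken wholly after randomization. The sensitivity analysis addresses that, although it drops patients without a screening score and uses an older measurement.
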